## 5. SAMPLE SIZE CALCULATIONS

A sample size of 31 subjects per group will have 90% power at a two-tailed significance level of 0.05 to detect a difference in the exploratory efficacy outcome EBV shedding of 70% in the treated group to 30% in the control group. With a dropout rate of approximately 30%, this study will require a total of 44 patients per group.

### Sample Size in Bronchoscopy sub study

The exploratory bronchoscopy sub-study will be voluntary for participants recruited to the EViSCO trial and thus no formal sample size calculation has been performed.

## 6. RANDOMISATION AND BLINDING

### 6.1 Randomisation

Eligible participants will be randomised using a 1:1 allocation ratio into the two groups. All researchers will be blinded to the sequence. After informed consent has been obtained and eligibility has been confirmed, the researcher will contact the clinical trials pharmacist who will assign a unique patient identifier in accordance with the randomisation schedule and confirm the study drug pack numbers to be dispensed.

The researcher will then complete the patient registration form and submit this to the NICTU who will confirm the registration of the patient and that the unique patient identifier assigned is in accordance with the randomisation schedule. The pharmacist will also confirm the study pack numbers to be dispensed at visit 2.

### 6.2 Blinding and Allocation Concealment

As a placebo controlled, double-blind trial, patients, clinicians and the Chief Investigator will be blinded to treatment allocation. Patients will be given a Patient Study Card when they are enrolled in the trial. This will include 24-hour contact details of their treating clinician in the event that the patient needs to contact their clinician. Emergency unblinding may be requested on safety grounds, or if the treatment decision for a patient could be influenced by the knowledge of what the patient is

taking as part of the trial. If there is justification to unblind a patient, emergency unblinding will be performed by the Belfast Trust on call pharmacist. In the event unblinding occurs, the patient may discontinue study drug but will remain on the trial unless they decide to withdraw. Where unblinding has occurred this should be fully documented by the site and the Sponsor and NICTU informed.

## **7. ANALYSIS PRINCIPLES**

The comparison of continuous outcomes will be carried out using t-tests followed by analysis of covariance adjusting for baseline FEV1 and other covariates if required. The mean and 95% confidence intervals will be reported. The categorical variables will be analysed using Fisher's Exact test or Chi-square test followed by logistic regression adjusting for baseline FEV1 and other covariates if required. The odds ratio and 95% confidence will be reported.

Statistical diagnostic methods will be used to check for violations of the assumptions, and transformations will be performed where required. Analyses will be on an intention-to-treat basis and all statistical tests will be at the 2-sided p-value of 0.05. A single final analysis is planned at the end of the trial.

Every effort will be made to minimise missing baseline and outcome data in this trial. The level and pattern of the missing data in the baseline variables and outcomes will be established by forming appropriate tables and the likely causes of any missingness will be investigated. This information will be used to determine whether the level and type of missing data has the potential to introduce bias into the analysis results for the proposed statistical methods, or substantially reduce the precision of estimates related to treatment effects. If necessary, these issues will be dealt with using multiple imputation or Bayesian methods for missing data as appropriate.

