## 13.2 Data Analysis

Analyses will be on an intention-to-treat basis and all statistical tests will be at the 2sided p-value of 0.05.

Comparison between groups for the primary safety outcome measure, incidence of SARs will be carried out using Fisher's exact test.

The primary efficacy outcome, suppression of EBV shedding will initially be analysed using chi-square test. Logistic regression will be used for adjusting for covariates if required. The comparison of continuous secondary/exploratory outcomes will be initially by t-tests followed by analysis of covariance or any other appropriate methodology if required. Statistical diagnostic methods will be used to check for violations of the assumptions, and transformations will be performed where required.

Correlations between changes in the biological markers measured and physiological and clinical outcomes will be assessed by appropriate graphical and statistical methods including Pearson's (or Spearman's) correlation coefficient.

A single final analysis is planned at the end of the trial. A detailed statistical analysis Plan will be written prior to the final statistical analysis.

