### 2.1 Primary outcome measure(s)

- The primary safety outcome is the incidence of serious adverse reactions (SARs).
- The primary efficacy outcome is suppression of Epstein-Barr virus in the sputum of subjects with COPD and will be assessed using quantitative PCR at baseline and 8 weeks.

EBV is a DNA virus that may be suppressed beyond detection, however, it may be reverse transcribed and so it is possible that there will be some detectable virus. For this reason we will define EBV suppression as a 90% reduction in the viral load.

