## 4. DEFINITION OF TERMS

Term	Definition
Adverse Event (AE)	Any untoward medical occurrence in a participant to whom a medicinal product has been administered including occurrences which are not necessarily caused by or related to that product.
Adverse Reaction (AR)	Any untoward and unintended response in a participant to an investigational medicinal product, which is related to any dose administered to that participant.
Unexpected Adverse Reaction (UAR)	An adverse reaction the nature and severity of which is not consistent with the Reference Safety Information.
Serious Adverse Event (SAE) Serious Adverse Reaction (SAR)	An adverse event or adverse reaction that:  results in death, is life-threatening, requires hospitalisation or prolongation of existing hospitalisation, results in persistent or significant disability or incapacity, consists of a congenital anomaly or birth defect, or any other important medical event(s) that carries a real, not hypothetical, risk of one of the outcomes above.
Suspected Serious Adverse Reaction (SSAR)	Any adverse reaction that is classed in nature as serious and is consistent with the Reference Safety Information (RSI)
Suspected Unexpected Serious Adverse Reaction (SUSAR)	Any adverse reaction that is classed in nature as serious and is not consistent with the Reference Safety Information
The EBV suppression	The EBV suppression is defined as 90% reduction in the viral load.
Per Protocol	The pre protocol population is defined as patients with overall study drug adherence of at least 70%
Overall Study Drug Adherence	Total number of tablets administered i.e. actual number of capsules taken / expected number of capsules taken
MMEF	Mid Expiratory Flow – MMEF 25-75% (L/s).

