### **7.1 Analysis of primary outcome**

#### **Safety**

The number of patients experiencing SAR in the two groups will be compared using Fisher's exact test, the relative risk and 95% confidence interval will be reported.

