### 8.3 Trial treatment

- Number of patients receiving at least one unit/dose of the drug, n(%) by treatment arm
- Duration of study drug (days), mean(SD) by treatment arm
- Overall compliance, mean(SD) by treatment arm
- Compliance, n(%) by treatment arm
- Time lapse between randomisation and study drug administration, mean(SD) by treatment arm
- Reason for study drug termination, n(%) by treatment arm
- Protocol Deviations/Violations, n(%) by treatment arm
- Premature withdrawals, n(%) by treatment arm

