	No	n (%)	n (%)	n (%)
Quantitative PCR Titre(copies)		xx.x (xx.x)	xx.x (xx.x)	xx.x (xx.x)

Relevant co-morbidities		n (%)	n (%)	n (%)
Pre-existing Cardiovascular issues		n (%)	n (%)	n (%)
Any exacerbations in past 12 months	Yes	n (%)	n (%)	n (%)
	No	n (%)	n (%)	n (%)
If Yes, Number of exacerbations in past 12 months		x.x (x.x to x.x)	x.x (x.x to x.x)	x.x (x.x to x.x)
If Yes, Number of exacerbations in past 12 months requiring steroids		x.x (x.x to x.x)	x.x (x.x to x.x)	x.x (x.x to x.x)
If Yes, Number of exacerbations in past 12 months requiring antibiotics		x.x (x.x to x.x)	x.x (x.x to x.x)	x.x (x.x to x.x)
If Yes, Number of exacerbations in past 12 months resulting in hospitalization		x.x (x.x to x.x)	x.x (x.x to x.x)	x.x (x.x to x.x)

Mean (SD) (or median (IQR)) presented for continuous variables and no. (%) for all categorical variables.

Table x.x: Treatment after Trial Entry Treatment Termination, Protocol Deviation

		Valaciclovir N = <n>	Placebo N = <n>
Number of patients who received at least one dose of treatment		n (xx.x%)	n (xx.x%)
Duration of study drug (days)		xx.x (x.x)	xx.x (x.x)
Overall compliance		xx.x (x.x)	xx.x (x.x)
Compliance	≥80%	n (xx.x%)	n (xx.x%)
	60-79%	n (xx.x%)	n (xx.x%)
	<60%	n (xx.x%)	n (xx.x%)
Time from randomisation to start of study drug (hours)		xx.x (xx.x to xx.x)	xx.x (xx.x to xx.x)
Reasons for termination of study drug			
1) Study Drug related AE		n (xx.x%)	n (xx.x%)
2) Study Drug related SAE		n (xx.x%)	n (xx.x%)
3) Study Drug Expiry Date		n (xx.x%)	n (xx.x%)
4) Patient Request		n (xx.x%)	n (xx.x%)
5) Clinician's Request		n (xx.x%)	n (xx.x%)
6) Other		n (xx.x%)	n (xx.x%)
Protocol deviations/ violations			
Eligibility		n (xx.x%)	n (xx.x%)
Consent		n (xx.x%)	n (xx.x%)
Study Drug Administration			
Did not receive allocated treatment a		n (xx.x%)	n (xx.x%)
Received treatment of other group b		n (xx.x%)	n (xx.x%)
Study drug omitted in error c		n (xx.x%)	n (xx.x%)
Study drug received in error		n (xx.x%)	n (xx.x%)
SAE reporting timelines		n (xx.x%)	n (xx.x%)
Visit outside schedule		n (xx.x%)	n (xx.x%)
Other		n (xx.x%)	n (xx.x%)
Premature Withdrawals			
Adverse Event		n (xx.x%)	n (xx.x%)
Serious Adverse Event		n (xx.x%)	n (xx.x%)
Protocol deviation/ non-compliance		n (xx.x%)	n (xx.x%)
Lost to Follow Up		n (xx.x%)	n (xx.x%)
Withdrawal of patient consent		n (xx.x%)	n (xx.x%)
Death		n (xx.x%)	n (xx.x%)

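### The primary safety comparison falls under the general intention-to-treat rule and no safety set is defined, although a serious adverse reaction is possible only in a dosed patient

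*SAP*

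**What the plan says.** - **Analysis basis.** SAP section 7: "Analyses will be on an intention-to-treat basis and all statistical tests will be at the 2-sided p-value of 0.05". Protocol 13.2: "Analyses will be on an intention-to-treat basis and all statistical tests will be at the 2sided p-value of 0.05"; its next sentence is the SAR comparison. Neither exempts safety.
- **Primary safety analysis.** SAP 7.1, Safety: "The number of patients experiencing SAR in the two groups will be compared using Fisher's exact test, the relative risk and 95% confidence interval" are to be reported. No analysis set is named there, and the safety table shell in Appendix 1 leaves its denominators blank.
- **Other populations.** SAP section 4 defines a per-protocol population (adherence of at least 70%), which SAP 7.1 uses for efficacy. There is no safety or as-treated population.
- **Definitions.** SAP section 4 defines an adverse event as "Any untoward medical occurrence in a participant to whom a medicinal product has been administered" and requires an adverse reaction to relate to a dose given to that participant. A SAR is a serious adverse reaction.
- **Timing.** Protocol 10.2.6 dates randomisation at dispensing, not at the first dose.
- **Exposure data.** SAP 8.3 tabulates "Number of patients receiving at least one unit/dose of the drug". The treatment table shell in Appendix 1 has deviation rows for not receiving the allocated treatment and for "Received treatment of other group".

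**The concern.** Intention to treat protects an efficacy comparison because it keeps the randomised groups intact and usually pulls the estimate towards no difference. For a superiority claim that is cautious. For safety the same pull works the other way: the hypothesis in Protocol 4.1 and SAP section 1 includes that the drug is safe, so dilution favours it.

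There are two routes. A patient who never took a dose cannot, by the plan's own definition, have a SAR, but still adds one to the denominator. A patient given the other arm's drug who then has a SAR is counted in the arm that did not cause it. At stake is how faithfully one of the two primary outcomes describes the risk in people exposed to valaciclovir. A second issue is that a statistician who sensibly used a dosed set would be departing from the written rule, possibly after seeing the allocation.

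**Working it through.** **Plan figures.** The documents give no SAR rate, no power for safety, and no expected number of undosed or crossover patients, so there is no safety figure to reproduce. The denominator comes from the efficacy sample size (Protocol 13.1, SAP section 5): 70% v 30%, two-sided 0.05, 90% power.

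- n per group = [1.96 × √(2 × 0.5 × 0.5) + 1.2816 × √(0.7 × 0.3 + 0.3 × 0.7)]² / 0.4² = (1.386 + 0.831)² / 0.16 = 30.7, so 31, as stated.
- With 30% dropout, 31 / 0.70 = 44.3. The plan states 44, which is used below.

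**Never-dosed patients.** Suppose x SARs occur in an arm of 44, of whom d took no dose (d is assumed). The risk is x/44 by intention to treat and x/(44 − d) among the dosed. The ratio of the first to the second is (44 − d)/44, so intention to treat lowers the risk by d/44, whatever x is.

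| d | relative reduction in the arm's SAR risk |
|---|---|
| 1 | 1/44 = 2.3% |
| 2 | 2/44 = 4.5% |
| 4 | 4/44 = 9.1% |
| 6 | 6/44 = 13.6% |

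For the relative risk, intention to treat multiplies the dosed-only value by (44 − d in valaciclovir)/(44 − d in placebo). Equal numbers undosed in the two arms leave it unchanged; it moves towards 1 only if more are undosed on valaciclovir.

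**Effect on Fisher's test when SARs are few.** I took 1, 2 or 3 SARs on valaciclovir and none on placebo, with every combination of 0 to 9 undosed per arm. The smallest two-sided p is 0.083 (3/35 v 0/44). No combination reaches 0.05.

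**A SAR in a crossover patient.** Assume one placebo-allocated patient took valaciclovir and had a SAR.

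- Three SARs, all on valaciclovir: by treatment received 3/45 v 0/43, p = 0.24; by intention to treat 2/44 v 1/44, p = 1.00. Neither is significant, but the relative risk by intention to treat is 2, while by treatment received there is no SAR on placebo at all.
- Six SARs, all on valaciclovir: by treatment received 6/45 v 0/43, p = 0.026; by intention to treat 5/44 v 1/44, p = 0.20. The test result changes, but only with a SAR risk of 6/45 = 13.3% on active drug, which nothing in the documents supports.

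**The case against.** **The plan is silent rather than wrong.** SAP 7.1 names no set for SARs, restates intention to treat only under Efficacy, and marks it as the primary analysis only in the efficacy table shell. This is fair as far as it goes, and a missing safety-set definition is an equally good description. But the general sentence in SAP section 7 has no exception, and in Protocol 13.2 it stands immediately before the SAR comparison. The natural reading covers safety.

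**Both cases may be rare.** A randomised patient already has drug dispensed, so few may go undosed. The pharmacist confirms pack numbers and the trials unit checks the identifier against the schedule (SAP 6.1). A reader might infer from the deviation row that the SAP expects crossover. It does not: an empty category in an example table is not an expectation. This objection stands and limits the size of the point.

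**The primary test would not move.** A reader might infer that one misplaced SAR would overturn the primary safety result. That needs something like six SARs against none. In the few-event setting that is more plausible for 88 patients, Fisher's conclusion stays the same. A marked shift in p from undosed patients likewise needs imbalance: 5/44 v 0/44 gives 0.055, and 5/40 v 0/40 still gives 0.055. Only one-sided non-dosing, such as 5/42 v 0/44, gives 0.024, and that owes much to the discreteness of the two-sided test. This objection stands too.

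**Adverse events are collected from enrolment** (Protocol 12.7), so an undosed patient might have one recorded. That sits awkwardly with the dosing-based definition of an adverse event, but it does not help for SARs, which still need a dose.

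**The exposure tables let a reader see any problem.** They show the counts but do not supply the corrected comparison.

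**Conclusion.** The point holds as a modest one. The stated rule puts the primary SAR comparison on an intention-to-treat basis, although the plan's own definitions confine SARs to dosed patients. The consequences are an arm-level SAR risk understated by d/44 (2.3% in relative terms for one undosed patient, 9.1% for four) and any crossover patient's SAR credited to the wrong arm. Both tend to dilute harm, though equal non-dosing in the two arms leaves the relative risk as it is.

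The numbers undosed and crossed over are assumptions throughout. If there are none of either, the two analyses are identical. The documents do not support a claim that the significance of the safety result is at risk: with one to three SARs against none and up to nine undosed per arm, no p falls below 0.08. The case for changing the plan is that the better method is standard, needs little, and should be fixed before unblinding.

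**What to change.** - In SAP 7, 7.1 and 8.5, and in Protocol 13.2, define a safety set: randomised patients who took at least one dose, grouped by treatment received. Apply it to SARs and all other safety outcomes. Changing the SAP alone would leave it in conflict with the protocol.
- Add a rule for a patient who received both drugs. Study drug is dispensed at visits 1 and 2 (Protocol 9.6), so an error could affect one supply only. One workable rule is to group with valaciclovir anyone who took any of it.
- Keep intention to treat for efficacy and show the intention-to-treat SAR table as a supplement.
- Fill in the denominators of the safety table shell accordingly, and reconcile the start of adverse event reporting in Protocol 12.7 with the dosing-based definition.

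The cost is one more analysis set and a short protocol clarification. Dosing and treatment received are already tabulated, and 31 and 44 per group are unaffected.

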### **7.1 Analysis of primary outcome**

#### **Safety**

The number of patients experiencing SAR in the two groups will be compared using Fisher's exact test, the relative risk and 95% confidence interval will be reported.

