#### 12.8 Adverse Event Reporting

Adverse events (AEs) associated with the patient's underlying medical condition should not be reported. However if the clinician responsible for the patients care determines that the patients change in health is related to the trial this should be reported. AEs that are not related to the underlying medical condition should be recorded within the CRF. The investigator should attempt to establish a diagnosis based on the subjects signs and symptoms and if possible record the diagnosis in the CRF as opposed to reporting the individual symptoms. All AEs should be treated appropriately and the action taken should be recorded in the CRF. Once an AE is detected it should be followed up until resolution or stabilisation, or the events are otherwise explained and the outcome recorded in the CRF.

An adverse reaction (AR) (i.e. an AE which is related to the administration of the study drug must be reported on the AE Form within the CRF. An unexpected adverse reaction (UAR) is an AE which is related to administration of the study drug and that is unexpected, in that it has not been previously reported in the approved RSI All UARs must be reported on the AE form within the CRF.

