## **13 STATISTICAL CONSIDERATIONS**

### 13.1 Sample Size

A sample size of 31 subjects per group will have 90% power at a two-tailed significance level of 0.05 to detect a difference in the primary efficacy outcome EBV shedding of 70% in the treated group to 30% in the control group. With a dropout rate of approximately 30%, this study will require a total of 44 patients per group.

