# 1. BACKGROUND AND DESIGN

The primary hypothesis is that treatment with valaciclovir is safe and will suppress Epstein-Barr virus in the sputum of patients with COPD.

This study seeks to establish if an antiviral therapy (valaciclovir) used to treat other herpes viruses is safe in patients with COPD. It also examines whether it is possible to suppress Epstein-Barr virus (EBV) in the airways of patients with COPD and examine important outcome measures including lung function and markers of airway inflammation in the blood and sputum.

The EBV suppression in COPD (EViSCO) study will be a randomised double-blind placebo-controlled clinical trial. The EViSCO trial will recruit subjects with COPD (GOLD classification 2 and 3) and EBV detectable in their sputum samples. Trial participants will receive either valaciclovir one gram three times daily or a matching placebo for a total of 8 weeks. EViSCO trial participants will be recruited to the sub-study on a voluntary basis

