### 8.4 Trial Outcomes

- **Primary Safety Outcome**
  - Incidence of serious adverse reactions (SARs) Serious adverse reaction, n(%) by treatment group, Relative risk 95% CI
- **Primary Efficacy Outcome**
  - Suppression of Epstein-Barr virus in the sputum of subjects with COPD from baseline to week 8
    - Number of patients experiencing suppression of Epstein-Barr virus, n(%) by treatment arm, odds ratio and 95% CI (Note: Suppression as defined by a 90% reduction in Quantitative PCR at week 8 when compared to baseline) followed by logistic

- regression adjusting for FEV1 and other covariates if required at baseline.
  - Descriptive results for sputum sample including; presence of EBV (yes/no) at baseline, week 4 and week 8, n(%) by treatment arm
- Change in viral load (Quantitative PCR) from baseline to week 8, mean(SD) by treatment arm, difference in mean with 95% CI\*
  - Descriptive results for quantitative PCR Titer(copies) at baseline, week 4 and week 8, mean(SD) by treatment arm
- Subgroup Analyses\*
  - Compliance ( $\geq 80\%$ , 60-79%,  $< 60\%$ ), n(%) by treatment arm, odds ratio and 99% CI from the treatment\*subgroup interaction model
- Sensitivity Analyses \*
  - Sensitivity analysis will be performed for the primary outcome excluding patients with a confirmed diagnosis of COVID-19 reported as an adverse event.
- **Secondary Outcomes**
  - **Lung function**
    - Change in FEV1 from baseline to week 8, mean(SD) by treatment arm, difference in mean with 95% CI
      - Exploratory Subgroup Analysis\*: EBV Suppression (as defined by 90% reduction in viral load) (Yes, No), mean(SD) by treatment arm, difference in mean and interaction term from ancova with 99% CI
    - Change in Forced Expiratory Volume in 1 second (FEV1 as a percentage of the predicted FEV1 value (%)) from baseline to week 8, mean(SD) by treatment arm, difference in mean with 95% CI
      - Exploratory Subgroup Analysis\*: EBV Suppression (as defined by 90% reduction in viral load) (Yes, No),

- mean(SD) by treatment arm, difference in mean and interaction term from ancova with 99% CI
- Change in FVC from baseline to week 8, mean(SD) by treatment arm, difference in mean with 95% CI
    - Exploratory Subgroup Analysis\*: EBV Suppression (as defined by 90% reduction in viral load) (Yes, No), mean(SD) by treatment arm, difference in mean and interaction term from ancova with 99% CI

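### The claim that valaciclovir is safe is tested only by a no-difference Fisher test and a relative risk for SARs, which at 44 per arm cannot support that claim; exact upper limits should carry the conclusion

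*SAP*

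**What the plan says.** SAP section 1 sets the hypothesis: "The primary hypothesis is that treatment with valaciclovir is safe and will suppress Epstein-Barr virus in the sputum of patients with COPD". Protocol 4.1 says the same. SAP 2.1 names the safety endpoint: "The primary safety outcome is the incidence of serious adverse reactions (SARs").

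The inferential plan for that endpoint is short. SAP 7.1 compares the number of patients with a SAR by Fisher's "exact test, the relative risk and 95% confidence interval will be reported". SAP 8.4 lists the output as "Serious adverse reaction, n(%) by treatment group, Relative risk 95% CI". Protocol 13.2 also names Fisher's exact test. SAP section 7 adds that "all statistical tests will be at the 2-sided p-value of 0.05".

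The only sample size calculation is in Protocol 13.1, repeated in SAP section 5. It concerns the virological outcome: "A sample size of 31 subjects per group will have 90% power at a two-tailed significance level of 0.05" for "EBV shedding of 70% in the treated group to 30% in the control group", raised to 44 per group for about 30% dropout.

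Neither document gives an expected SAR rate, an excess to be ruled out, a margin, a decision rule, an exact interval per arm, a risk difference, or a rule for zero counts.

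On event capture, Protocol 12.8 says: "Adverse events (AEs) associated with the patient's underlying medical condition should not be reported". It makes an exception where the responsible clinician judges the change to be related to the trial. Protocol 12.9 requires SAEs to go to the sponsor within 24 hours and states no exemption for the underlying disease. Protocol 12.7 has all SAEs in the reporting period followed up.

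**The concern.** Fisher's test takes no difference as its null hypothesis. It can give evidence of harm, but failure to reject is not evidence that harm is absent. Half of the primary hypothesis is a positive claim of safety, and the plan supplies no other criterion by which to reach it.

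SARs are serious and also judged related to the drug, so counts may be very small. Two things then follow. The test will be negative across a wide range of true harm. The relative risk, which is the only effect measure named, may also have a zero in its denominator. The report could then offer a non-significant p-value and an unusable ratio in answer to one of the trial's two primary questions, with nothing to tell the reader which SAR rates the data exclude.

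The all-cause SAE comparison is the natural check, because it does not depend on a causality judgement. Its value depends on whether admissions for COPD enter it, and the protocol does not settle that.

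**Working it through.** **Inputs.** From the documents: 44 per arm, 1:1 allocation, two-sided 0.05, Fisher's exact test (Protocol 13.1 and 13.2; SAP sections 5, 6.1, 7 and 7.1). The documents give no SAR rates, so every rate below is an assumption and a range is shown.

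**1. The plan's own figure.** With 70% v 30% and pooled variance, n = [1.96 × √(2 × 0.5 × 0.5) + 1.2816 × √(0.7 × 0.3 + 0.3 × 0.7)]² / 0.4² = (1.386 + 0.831)² / 0.16 = 30.7, so 31 per group. Then 31 / 0.70 = 44.3, against the stated 44. The calculation reproduces, but it does not concern SARs.

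**2. Smallest significant split.** With no placebo SARs and k on valaciclovir, two-sided p = 2 × C(44,k) / C(88,k).
- k = 5: 2 × 1,086,008 / 39,175,752 = 0.055
- k = 6: 2 × 7,059,052 / 541,931,236 = 0.026

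Six events are needed, which is 6/44 = 13.6% against 0%. Against one placebo SAR, 7 events are not enough (p = 0.058); 8 are needed.

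**3. Power.** Summing the two binomial probabilities over every outcome with Fisher p ≤ 0.05, at 44 per arm:

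| Assumed SAR rate, valaciclovir v placebo | Power |
|---|---|
| 3% v 1% | 0.1% |
| 5% v 1% | 1.4% |
| 10% v 2% | 14.3% |
| 10% v 1% | 19.8% |
| 15% v 1% | 53.6% |
| 20% v 1% | 80.6% |

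**4. When the ratio fails.** The relative risk is infinite or undefined when placebo has no SARs. The probability is (1 − p)^44:
- p = 1%: 0.99^44 = 64%
- p = 2%: 0.98^44 = 41%
- p = 5%: 0.95^44 = 10%

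Where it can be calculated from such counts it says little. For 1 v 1 the relative risk is 1.0, with a log-based 95% interval of 0.06 to 15.5.

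**5. What zero events would exclude.** The Clopper-Pearson two-sided 95% upper limit for 0/n is 1 − 0.025^(1/n).
- n = 44: 8.0% (one-sided 95%: 1 − 0.05^(1/44) = 6.6%)
- n = 31: 11.2%

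For 0 v 0 at 44 per arm, the Newcombe interval for the risk difference runs from about −8.0 to +8.0 points. To exclude a 5% SAR rate with zero events would need ln(0.025) / ln(0.95), rounded up to 72 patients in that arm.

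**6. Event capture.** Protocol 12.9 defines an SAE as an AE that meets a seriousness criterion, and inpatient admission of any length is one (12.1, 12.3). Read through 12.8, an admission put down to COPD might not be reported as an AE and so might never become an SAE. Read alone, 12.9 requires it. The text permits both readings.

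**The case against.** **The plan nowhere says that a non-significant test means safe.** This is correct. A reader might infer it, because the hypothesis asserts safety and the test is the only inference offered, but no section states it. The plan also reports n (%) per arm and a confidence interval, not a p-value alone. What stands is that it gives no other criterion.

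**SAR incidence is always estimable.** Also correct. A reader might take zero counts to mean that the endpoint cannot be estimated, but only the ratio is affected. A zero on valaciclovir alone gives a relative risk of 0, which is defined. The SAP does not name an interval method, and a score interval copes with one zero cell: for 5 v 0 the lower limit is about 1.35. At a 5% placebo rate the problem would be uncommon.

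**Low power for rare events is inherent in an 88-patient trial, and no reanalysis adds power.** True, and a very large excess would probably be detected. The proposal does not seek power; it makes the report state what was and was not excluded.

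**Wider safety comparisons are already planned.** SAP 8.5 and its safety table compare AEs, ARs, SAEs, SUSARs and fatal events by arm. SAP 8.4 compares exacerbations to week 12. The DMEC reviews safety. These support the assessment, but none sets a criterion for the primary safety claim.

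**COPD admissions are not shown to be lost.** A reader might conclude from Protocol 12.8 that they would be missing from the SAE table. The documents do not support that: 12.9 carries no such exemption, 12.7 follows all SAEs, 12.8 has its own exception, and exacerbations are documented at every contact.

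**Conclusion.** The point holds as a mismatch between claim and analysis. With 44 per arm, a non-significant Fisher test on SARs is compatible with excesses up to roughly 10 percentage points: power is 20% or less at 10% v 1% or 2%. It cannot support the statement that valaciclovir is safe. Even the most favourable result, no SARs in 44 patients, excludes only rates above about 8.0%.

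The power and zero-count probabilities rest on assumed SAR rates. The significance threshold and the exact limit do not; they need only 44 patients per arm with safety data. Protocol 10.1.5 has safety contacts continue after early stopping, so the safety denominator may stay nearer 44 than 31. At 31, the zero-event limit is 11.2%.

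The overlap between Protocol 12.8 and 12.9 is an ambiguity to resolve, not a demonstrated loss of events.

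**What to change.** In SAP 7.1 and 8.4:

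- Make the primary safety estimate the SAR incidence per arm with Clopper-Pearson 95% limits, and the risk difference with one score-type 95% interval named in advance (Newcombe or Miettinen-Nurminen).
- Keep Fisher's test as supportive. State that the intervals lead, because the two can disagree at the margin: for 5 v 0, Fisher p is 0.055 although a score interval for the ratio excludes 1.
- Give the relative risk only when both arms have events.
- State that the safety conclusion will quote the upper limits and will not rest on a non-significant p-value.
- Name the all-cause SAE comparison already listed in SAP 8.5 as the key supporting analysis.

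In the protocol, reconcile 12.8 with 12.7 and 12.9, so that it is explicit whether COPD admissions enter the SAE comparison.

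The cost is minor SAP wording, one protocol clarification and a more modest safety claim. No patients are added and the design does not change.
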